4.5.2. Adverse Events

Adverse events analyses including the analysis of adverse events (AEs), Serious adverse events (SAEs) and other significant AEs will be based on GSK Core Data Standards. Dose modifications, dose interruptions, dose reduction, and dose delays will be listed according to GSK Oncology Data Standards. The details of the planned displays are provided in OPS document.

AEs will be coded using the standard MedDRA v.21.1. and grouped by system organ class. AEs will be graded by the investigator according to the NCI-CTCAE (version 5.0).

Summary of all Adverse Events and Drug related Adverse events by System Organ Class and Preferred Term and Maximum Grade will be reported. Summary of Grade 3-5 AEs and drug related Grade 3-5 AEs that occurred in $\geq 5\%$ of participants will be provided by Overall frequency.

A summary of non-serious AEs that occurred in strictly 5% of the participants or above will be provided (no rounding for the percentage will be used in terms of 5% threshold, e.g. events with 4.9% incidence rate should not be included in this table).

A summary of number and percentage of participants with any adverse events by maximum grade will be produced. AEs will be sorted by PT in descending order of total incidence. The summary will use the following algorithms for counting the participant:

- **Preferred term row:** Participants experiencing the same AE preferred term several times with different grades will only be counted once with the maximum grade.
- **Any event row:** Each participant with at least one adverse event will be counted only once at the maximum grade no matter how many events they have.

- Summary of non-serious drug related adverse events by overall frequency by PT will be produced.

All AEs will be listed. Additionally, a listing of subject IDs for each individual AE will be produced. Listing of relationship of adverse event System Organ Class (SOC), Preferred term (PT) and verbatim text will be produced.

AEs with missing date of onset will be considered treatment emergent.

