6.2.2.3. Treatment Emergent Flag for Adverse Events

Flag	Definition
Treatment Emergent	
Non-serious AEs
 
In general, all AEs with a start date after treatment are considered emergent regardless of AE start date is before or after treatment stop date.
 
 • If AE onset date is on or after treatment start date & on or before treatment stop date + 30 days 
 ◦ Study Treatment Start Date \leq AE Start Date \leq Study Treatment Stop Date + 30 days ◦ AE Start Date is missing 
Serious AE/AESI
 
 ◦ If AE onset date is on or after treatment start date & on or before treatment stop date + 30 days Study Treatment Start Date \leq AE Start Date \leq Study Treatment Stop Date + 30 days ◦ AE Start Date is missing 
Missing AE Start Date will be imputed following rules in Section 12.7.2.1 for determining Treatment Emergent AEs.

NOTES:

- [If the study treatment stop date is missing, then the AE will be considered to be On-Treatment.]
- If the study treatment stop date is missing, then the AE will be On-Treatment.
- Time of study treatment dosing and start/[stop] time of AEs should be considered, if collected.

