Missing start day	
 If study treatment start date is missing (i.e. participant did not start study treatment), then set start date = 1st of month. Else if study treatment start date is not missing: 
 If month and year of start date = month and year of study treatment start date, then 
 If stop date contains a full date and stop date is earlier than study treatment start date, then set start date= 1st of month. 		

Element	Reporting Detail	
	Missing start day and month	
 ▪ Else set start date = study treatment start date. 
 ○ Else set start date = 1st of month. • If study treatment start date is missing (i.e. participant did not start study treatment), then set start date = January 1. • Else if study treatment start date is not missing: 
 ○ If year of start date = year of study treatment start date, then 
 ▪ If stop date contains a full date and stop date is earlier than study treatment start date, then set start date = January 1. ▪ Else set start date = study treatment start date. ○ Else set start date = January 1.
	Missing stop day	Last day of the month will be used.
	Missing stop day and month	No Imputation
	Completely missing start/end date	No imputation
Concomitant Medications/ Blood Supportive Products		
 • Partial dates for any concomitant medications recorded in the CRF will be imputed using the following convention:
	Missing start day	
 • If study treatment start date is missing (i.e. participant did not start study treatment), then set start date = 1st of month. • Else if study treatment start date is not missing: 
 ○ If month and year of start date = month and year of study treatment start date, then 
 ▪ If stop date contains a full date and stop date is earlier than study treatment start date, then set start date= 1st of month. ▪ Else set start date = study treatment start date. ○ Else set start date = 1st of month.
	Missing start day and month	
 • If study treatment start date is missing (i.e. participant did not start study treatment), then set start date = January 1. • Else if study treatment start date is not missing:

Element	Reporting Detail	

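### The treatment-emergent rules flag some adverse events whose recorded stop date shows they ended before first dose

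*SAP*

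**What the plan says.** Section 4.5.2 sets the general rule: "AEs with missing date of onset will be considered treatment emergent". The flag table in 6.2.2.3 bases the flag on onset ("If AE onset date is on or after treatment start date & on or before treatment stop date + 30 days") and lists "AE Start Date is missing" as a condition sufficient on its own, for non-serious events and for serious events or AESIs alike. Neither place mentions the stop date. The same table adds "Missing AE Start Date will be imputed following rules in Section 12.7.2.1", but this SAP has no such section.

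Section 6.2.6 holds the date rules for adverse events:

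- For a partial onset in the month or year of first dose, it asks a question about the stop date: "If stop date contains a full date and stop date is earlier than study treatment start date". If the answer is yes, the start goes to the beginning of that month or year, so the event is not emergent. Otherwise: "Else set start date = study treatment start date".
- For a stop date with only the day missing: "Last day of the month will be used".
- A stop date known to year only is not imputed.
- The row headed "Completely missing start/end date" prescribes no imputation.

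**The concern.** The check in 6.2.6 shows that the SAP accepts a principle: an event known to have ended before treatment is not treatment emergent. Two other rules defeat it.

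First, a completely missing onset bypasses the check, even when a complete stop date settles the timing. Second, the check ignores a stop date given as month and year, even when every day of that month precedes first dose. In the second case the derived start can fall after the derived stop.

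Counting an event as emergent is a sensible default when its timing is unknown. In these records the timing relative to first dose is known. At stake are the phase assignment, the treatment-emergent flag and any adverse event summary filtered on that flag.

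**Working it through.** The SAP gives no figure on this point, so there is none to reproduce. The check applies the rules of 4.5.2, 6.2.2.3 and 6.2.6 literally to dated examples.

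**Example of the inversion.** Assume first dose on 20 Mar 2021, onset recorded as 2021 and stop recorded as Feb 2021. The stop is not a full date, so the check does not fire and the start becomes 20 Mar 2021. The stop becomes 28 Feb 2021. The start is 20 days after the stop, and the event is flagged emergent.

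**Comparison of cases.** Assumed first dose 15 Jun 2020, last dose 15 Sep 2020.

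| Recorded onset | Recorded stop | Derived start | Derived stop | Flag |
|---|---|---|---|---|
| missing | 10 Jun 2020 | none | 10 Jun 2020 | emergent |
| missing | Mar 2020 | none | 31 Mar 2020 | emergent |
| missing | 2019 | none | none | emergent |
| 2020 | Mar 2020 | 15 Jun 2020 | 31 Mar 2020 | emergent, start after stop |
| 2020 | 10 Mar 2020 | 1 Jan 2020 | 10 Mar 2020 | not emergent |
| Jun 2020 | 10 Jun 2020 | 1 Jun 2020 | 10 Jun 2020 | not emergent |
| Jun 2020 | Jun 2020 | 15 Jun 2020 | 30 Jun 2020 | emergent, order unknown |

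The first four events ended before first dose on any reading of the record, yet are flagged. The first and sixth rows share a stop date and differ only in how much of the onset is recorded; the less complete record changes the classification.

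**All event dates.** Take every true start and stop between 1 Jan and 14 Jun 2020, the 166 days before first dose: 166 × 167 / 2 = 13,861 pairs, all of them pre-treatment. Mask the dates in each pattern and apply the rules.

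- Missing onset, any stop date: 100% flagged emergent.
- Year-only onset, month-year stop: 100% flagged. The start falls after the stop whenever the stop month is January to May (152 days): 152 × 153 / 2 = 11,628 pairs, and 11,628 / 13,861 = 83.9%.
- Full or partial onset, full stop: 0% flagged.

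With the check extended as proposed under the fix:

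- Missing onset, full stop: 100% falls to 0%.
- Missing onset or year-only onset, month-year stop: 100% falls to (13,861 − 11,628) / 13,861 = 16.1%. These stops lie in the month of first dose, where the order cannot be determined and the conservative default rightly stays.
- The start-after-stop records disappear.

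These percentages describe how the rules behave over an even grid of dates. They do not estimate how often such records will occur.

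**Effect on a table row.** Section 5 allows at most 15 participants per ipilimumab dose level. One participant newly counted in a row adds 1/15 = 6.7 percentage points to a column of 15, or 1/10 = 10 points to a column of 10.

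**The case against.** The strongest reply is that treating a missing onset as emergent is a common and conservative default. That stands for unknown timing, but it does not cover records whose stop date settles the timing, and 6.2.6 already makes the distinction for partial onsets.

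A programmer might impute the stop to month end first and treat the result as a full date, which would remove the inversion. The SAP does not fix that order, and its condition reads most naturally as referring to the recorded date. Nor would this help a completely missing onset.

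The inversion is narrow. It needs a year-only onset in the first-dose year and a month-year stop in an earlier month; it cannot arise when only the onset day is missing. Both problems also require pre-dose events to be recorded as adverse events, and when collection starts is a matter for the protocol, which is not at hand. The stop-before-treatment check itself, however, presupposes that such records can exist.

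A reader might infer that pre-treatment events contaminate the primary endpoint. The SAP does not support that. Section 4.2 names DLT rate, AEs and SAEs, not treatment-emergent counts, and 4.5.2 restricts no named table to flagged events. DLTs are tied to a 21-day window and investigator attribution, and no effect on them is shown.

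A reader might also take 6.7 points as the effect of each misflagged record. It is not, because 4.5.2 counts a participant once per preferred term.

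Finally, the inverted dates do not reach reported durations: 6.2.6 excludes imputed dates from study day, time to onset and duration, and listings show dates as captured.

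**Conclusion.** The rules as written misclassify two identifiable kinds of record: events with no onset date whose stop precedes first dose, and events with a year-only onset in the first-dose year and a month-year stop in an earlier month. This follows from the text, given the natural reading that a full stop date means one recorded in full.

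The consequence is limited to the phase and treatment-emergent flag and to any summary filtered on that flag; which displays are filtered cannot be read from this SAP. The number of affected records cannot be estimated, since no rate of missing dates is given, and is probably small. The effect in a filtered table is about 6.7 points per newly counted participant at n = 15, and zero if that participant is already in the row.

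A related and firmer inconsistency lies in the same place: 6.2.2.3 promises imputation of missing start dates under a section that does not exist, while 6.2.6 says completely missing dates are not imputed. Overall this is a minor point, worth correcting because the correction is nearly free.

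**What to change.** - **4.5.2 and 6.2.2.3:** state that an adverse event with missing onset is treatment emergent unless its recorded stop date, whether full, month-year or year-only, necessarily falls before the study treatment start date.
- **6.2.6, adverse events:** impute a stop date with a missing day to month end before the stop-before-treatment check, and use the result in that check. Compare a year-only stop by year alone, leaving it unimputed as now. Add a safeguard that an imputed start may not exceed the stop date.
- **6.2.2.3:** replace the reference to Section 12.7.2.1 with 6.2.6, and make clear that partial starts are imputed there, while completely missing starts are not imputed and are classified by the flag rule alone.

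The cost is a few clauses and a small change to the flag derivation. No new data are needed, and the conservative default is kept wherever the order of event and first dose is unknown. If the database contains no record of either kind, no output changes.

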4.5.2.1. Adverse Events of Special Interest

No AESI are reported in part 1.

4.5.2.2. COVID-19 Assessment and COVID-19 AEs

Confirmed, probable and suspected COVID 19 cases will be summarized and listed. Visits impacted by COVID-19 Pandemic will be summarized. Number of subjects with missed visits, site visits with one or more assessment missed, remote visit with no assessments missed and remote visit with one or more assessments missed will be summarized with primary reason for the impact.

4.5.3. Additional Safety Assessments

4.5.3.1. Deaths and Serious Adverse Events

All deaths will be listed to provide participant-specific details on participants who died.

All SAEs will be tabulated based on the number and percentage of participants who experienced the event. The summary table will be displayed in descending order of total incidence by SOC and PT. Summary of Drug related SAE, fatal SAE, drug-related fatal SAE will also be produced

A study treatment-related SAE is defined as an SAE for which the investigator classifies the relationship to study treatment as “Yes”. A worst-case scenario approach will be taken to handle missing data, i.e. the summary table will include events with the relationship to study treatment as ‘Yes’ or missing.

SAEs are included in the listing of all adverse events.

A listing of reasons for considering an SAE will be provided.

4.5.3.2. Adverse Events Leading to Discontinuation of Study Treatment and/or Withdrawal from the Study and Other Significant Adverse Events

Following listings will be provided,

- AEs Leading to Discontinuation of Study Treatment
- AEs Leading to Withdrawal from the Study

An AE leading to dose modification is an AE for which the action with respect to dosing is recorded as reduction or interruption of dose. AEs that lead to both a dose modification and a discontinuation of study treatment will only appear in the AEs leading to discontinuation of study treatment summary.

4.5.3.3. Pregnancies

While pregnancy itself is not considered to be an AE or SAE, any pregnancy complication or elective termination of a pregnancy for medical reasons will be recorded as an AE or SAE as described in the protocol. If subjects become pregnant while on the study, the information will be included in the narratives and no separate table or listing will be produced.

4.5.3.4. Laboratory Data

Laboratory grades will be reported using the Common Terminology Criteria for Adverse Events (CTCAE v5.0). The assessment of laboratory toxicities will examine the following laboratory tests performed by local laboratories:

Laboratory Assessments	Parameters			
Hematology	RBC Indices	WBC count with Differential	Platelets	
	Hemoglobin	Neutrophils		
	Hematocrit	Lymphocytes		
	RBC count	Monocytes		
		Eosinophils		
		Basophils		
Clinical Chemistry	BUN ^a	Potassium	Bilirubin	AST (SGOT)
	Creatinine ^b	Sodium	Total protein	ALT (SGPT)
	Glucose	Calcium	Albumin	Alkaline phosphatase
	LDH			
Coagulation	INR or PT			
	PTT/aPTT			
Cardiac Function	Troponin I or Troponin T			
Thyroid Function	Thyroid stimulating hormone Free T4 Free T3 (when clinically indicated)			
Routine Urinalysis	Specific gravity pH, glucose, protein, blood and ketones by dipstick (Note: routine urinalysis by method other than dipstick is acceptable, in accordance with local practice).			
Other Screening Tests	Hepatitis B surface antigen (HBsAg) Hepatitis C (Hep C antibody) ^c Serum β-hCG Pregnancy test (for women of child bearing potential)			

Abbreviations: ALT = alanine aminotransferase; AST = aspartate aminotransferase; β-hCG = beta-human chorionic gonadotropin; BUN = blood urea nitrogen; HBsAg = Hepatitis B surface antigen; RBC = red blood cells; SGOT = serum glutamic oxaloacetic transaminase; SGPT = serum glutamic pyruvic transaminase; T3 = triiodothyronine; T4 = thyroxine; WBC = white blood cells; INR = International Normalized Ratio; PT = Prothrombin Time; aPTT = Activated Partial Thromboplastin Time

- Required if local laboratory testing is available
- Creatinine clearance is also required to be calculated using the formula provided in Appendix 9 of the protocol.
- Participants with positive Hepatitis C antibody due to prior resolved disease can be enrolled, only if a confirmatory negative Hepatitis C RNA test is obtained. Hepatitis C RNA Test is optional with negative Hepatitis C antibody test.

d. Coagulation factors (PT/INR and aPTT/PTT) should be tested as part of the screening procedures for all participants. Any participant receiving anticoagulant therapy should have coagulation factors monitored closely throughout the study

Change from baseline by scheduled visits will be summarised using mean, median, standard deviation, minimum, and maximum.

Summaries of worst case grade increase from baseline grade will be provided for all the lab tests that are gradable by CTCAE v5.0. These summaries will display the number and percentage of participants with a maximum post-baseline grade increasing from their baseline grade. Any increase in grade from baseline will be summarized along with any increase to a maximum grade of 3 and any increase to a maximum grade of 4. Missing baseline grade will be assumed as grade 0. In addition, the summary will include grade increase from baseline by scheduled visits. For laboratory tests that are graded for both low and high values, summaries will be done separately and labelled bi-direction, e.g. sodium will be summarized as hyponatremia and hypernatremia.

For lab tests that are not gradable by CTCAE v5.0, summaries of worst case changes from baseline with respect to normal range will be generated. Decreases to low, changes to normal or no changes from baseline, and increases to high will be summarized at each scheduled visit as well as for the worst case post-baseline. If a participant has a “Decrease to low” and an “Increase to high” during the same time interval, then the participant is counted in both the “Decrease to Low” category and the “Increase to High” category. In addition, the summary will include worst case changes from baseline with respect to normal range by scheduled visits.

Separate summary tables for hematology and chemistry laboratory tests will be produced.

Listing of Laboratory values of Potential Clinical Importance and listing of all laboratory values for any value of potential clinical importance will be produced

A separate listing of laboratory data with character values will also be provided. Unless otherwise specified, the denominator in percentage calculation at each scheduled visit will be based on the number of participants with non-missing value at each visit.

Urinalysis Results will be summarised. Worst-case Urinalysis Results Post-Baseline Relative to Baseline will be summarised

A character lab value starting with ‘<X’ or ‘>X’ will be displayed in listings but will not be imputed with a numeric value thus will not be included for summaries.

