6.2. Appendix 2 Data Derivations Rule

6.2.1. Criteria for Potential Clinical Importance

To identify values of potential clinical importance, National Cancer Institute Common Terminology Criteria for Adverse Events (NCI-CTCAE v [5.0]) will be used to assign grades for laboratory parameters including clinical chemistry, hematology, liver function tests, QTc (Fridericia's) values, LVEF and vital signs (heart rate, blood pressure, temperature).

Reference ranges for all laboratory parameters collected throughout the study are provided by the laboratory. A laboratory value that is outside the reference range is considered either high abnormal (value above the upper limit of the reference range) or low abnormal (value below the lower limit of the reference range). Note: a high abnormal or low abnormal laboratory value is not necessarily of clinical concern. The laboratory reference ranges will be provided on the listings of laboratory data. Clinical laboratory test results outside of the reference range will be flagged in the listings.

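### The exclusion of `<X` and `>X` laboratory values is not limited to numeric statistics, so the grade and normal-range tables can omit results whose category is already known

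*SAP*

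**What the plan says.** SAP Section 4.5.3.4 describes three kinds of laboratory output, based on "the following laboratory tests performed by local laboratories".

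- **Numeric:** "Change from baseline by scheduled visits will be summarised using mean, median, standard deviation, minimum, and maximum".
- **CTCAE grade:** tables counting participants with "a maximum post-baseline grade increasing from their baseline grade". In these, "Any increase in grade from baseline will be summarized", with further rows for increases to grade 3 and to grade 4. A baseline grade that is missing is taken as grade 0.
- **Normal range**, for tests that CTCAE does not grade: "Decreases to low, changes to normal or no changes from baseline, and increases to high will be summarized at each scheduled visit", and also for the worst post-baseline result.

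By-visit percentages use participants with a non-missing value at that visit as the denominator. The section ends with the rule that a character value beginning with `<X` or `>X` "will be displayed in listings but will not be imputed with a numeric value thus will not be included for summaries". Character values also get their own listing.

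Section 6.2.1 defines abnormality purely by position: "A laboratory value that is outside the reference range is considered either high abnormal (value above the upper limit of the reference range"), with low abnormal as the mirror image at the lower limit. It adds that "Clinical laboratory test results outside of the reference range will be flagged in the listings".

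**The concern.** The reason given for the exclusion is that no number is assigned. That reason fits the mean, median, standard deviation, minimum and maximum. It does not fit a table that needs only low, normal or high, or a grade. The exclusion sentence names no type of summary, and Section 4.5.3.4 uses that word for its category tables as well. A programmer who follows the text would therefore remove these values from all three kinds of output.

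A result beyond a reporting limit may be the most extreme one a participant has. If it is left out, an abnormality that is known with certainty is missing from the table, and the error runs towards understating laboratory toxicity. The SAP also does not say whether such a value counts as non-missing in the by-visit denominator, or what baseline category it gives.

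**Working it through.** The SAP states no figure that depends on this rule, so there is nothing to reproduce. The check is logical, followed by a short illustration of size.

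**Step 1. When does X settle the normal-range category?** Let L and U be the reference limits and v the unknown true value.

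- `<X` means v < X. If X ≤ L, then v < L: low.
- `>X` means v > X. If X ≥ U, then v > U: high.
- Otherwise X alone does not establish low or high.

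With an example range of 10 to 20 (my numbers, not the SAP's):

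| Reported | Category |
|---|---|
| `<5` | low, settled |
| `<10` | low, settled |
| `<15` | not settled |
| `>15` | not settled |
| `>20` | high, settled |
| `>25` | high, settled |

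Some character values, not all, therefore have a known category without any imputation.

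**Step 2. When does X settle a grade?** Take a test graded on its high side with rising cut points c1 to c4, where grade g begins above c_g.

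- `>X` with c2 ≤ X < c3 means grade 2 or higher. If the baseline grade is 0 or 1, an increase is certain, but the grade 3 and grade 4 rows are not settled.
- `>X` with c3 ≤ X < c4 means grade 3 or 4. An increase from a lower baseline is certain, but which of the two rows applies is not.
- `>X` with X ≥ c4 means grade 4, settled.

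The grade tables thus need one more convention than the normal-range tables, because X may give only a minimum grade.

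**Step 3. Which cells change?**

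- *By visit:* a participant is lost from the cell if the only value at that visit is a character value, even when other visits have numeric results.
- *Worst case:* nothing changes if the participant also has a numeric post-baseline value in the same or a worse category. Otherwise the participant is lost from the cell.

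**Step 4. Size for one affected participant.** Section 5 gives a maximum of 15 per dose level. Section 1.2 gives 10 to 15 per combination. Suppose one participant's only qualifying result is a settled character value.

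| n | As written | Classified | Difference |
|---|---|---|---|
| 15 | 0/15 = 0% (exact 95% upper limit 21.8%) | 1/15 = 6.7% (0.2% to 31.9%) | 6.7 points |
| 10 | 0/10 = 0% (upper limit 30.8%) | 1/10 = 10.0% (0.3% to 44.5%) | 10.0 points |

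If the value is also dropped from the by-visit denominator and k of the other 14 participants are abnormal, the difference is (k+1)/15 − k/14 = (14 − k)/210. That is 14/210 = 6.7 points at k = 0 and less for larger k. Two affected participants at one dose level would give 2/15 = 13.3 points. The counts of one and two are illustrations, since the SAP gives no frequency.

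**The case against.** The best reply is that the sentence ties the exclusion to the absence of a numeric value, so the authors may have had only the numeric statistics in mind. That reading is available. But the sentence does not say so, and nothing else in the SAP provides for grading or classifying a character value. If it is what was meant, the edit below simply records it.

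Second, the convention is pre-specified and open. Every value stays in the listings, with a separate listing for character values, and at 15 or fewer participants per dose level a reader can inspect each one. This stands, and it is the main reason for giving the point little weight.

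Third, 6.7 points is just 1/15 and would follow from losing any participant for any reason. That also stands. It shows how sensitive a cell is, not how large an expected bias is.

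Three stronger readings are tempting but not supported:

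- *That the SAP contradicts itself because a listing may flag a result the table omits.* Section 6.2.1 governs flags in listings, and Section 4.5.3.4 says openly that these values are listed and not summarised. A listing that shows more than a table is the declared design.
- *That an abnormal character baseline becomes grade 0, producing a false grade increase, or that by-visit denominators shrink.* Either would follow only if character values were treated as missing. The SAP does not say that they are.
- *That the main safety conclusions are at risk.* Section 1.1 does list laboratory changes among the Part 1 primary endpoints, but Section 4.2 narrows the analysis to DLTs, AEs and SAEs. DLTs rest on investigator assessment, and no decision rule in the SAP uses these tables.

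**Conclusion.** The point holds as a fault in scope. The exclusion is worded for all summaries, its stated reason applies only to numeric ones, and under the SAP's own definitions some of the excluded results have a known category. The grade and normal-range tables can therefore understate abnormality.

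The impact is minor. For each affected participant it is zero in a worst-case cell when a numeric value in the same or a worse category exists, and otherwise 6.7 points at n = 15 or 10.0 points at n = 10. This assumes that at least one settled character value occurs in a tabulated test as the only qualifying result, and the SAP does not show whether that happens. The tables are descriptive, the arm is being closed in Part 1, and no value is lost from the listings. The change is still worth making, because it is cheap and removes an avoidable one-directional error. The rules for repeat measurements in Section 6.2.5 are a separate matter and play no part in this conclusion.

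**What to change.** In Section 4.5.3.4:

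1. Limit the exclusion of `<X` and `>X` values to numeric statistics: mean, median, standard deviation, minimum and maximum.
2. In the normal-range and grade tables, classify a character value, baseline or post-baseline, wherever X settles the category, and count it as non-missing.
3. Where X gives only a minimum post-baseline grade, count the participant in the row for any increase if that minimum exceeds the baseline grade. Count the participant in the grade 3 or grade 4 row only if X settles that grade.
4. Footnote the values that cannot be classified. Do not let an unclassifiable character baseline pass silently as missing and hence grade 0; if that convention is used, footnote it.

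The cost is a few sentences, one or two table footnotes, and a programming check of each X against the local laboratory's reference range and the CTCAE cut points. With at most 15 participants per dose level this is a small task.
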